### **6.1.1 Screening Visit (-21 to -1 days before start of treatment)**

- Informed consent
- Inclusion and exclusion criteria
- Demographics
- Medical history
- Adverse events
- Concomitant medications
- QOL assessment
- Height
- Weight
- Vital signs
- Complete physical exam
- 12-lead ECG (may be performed on C1D1)
- ECOG PS (may be performed on C1D1)
- CBC with differential
- TSH (may be performed on C1D1)
- Complete serum chemistry
- Pregnancy test
- SPEP and serum immunofixation
- UPEP (24-hr urine) and urine immunofixation
- Quantitative Ig levels
- Serum FLC
- LDH and  $\beta$ 2-microglobulin
- Skeletal survey
- Plasmacytoma assessment
- Bone marrow biopsy and aspirate

### **6.1.2 Treatment Phase**

#### **6.1.2.1 Visit 1 (baseline; Cycle 1 Day 1)**

- Medication dispensation
- Adverse events
- Concomitant medications
- Dose intensity
- QOL assessment
- Weight
- Vital signs
- Symptom-directed physical exam
- 12-lead ECG (may be performed on Screening visit)
- ECOG PS (may be performed on Screening visit)
- CBC with differential
- TSH (may be performed on Screening visit)
- Complete serum chemistry
- Pregnancy test

- SPEP and serum immunofixation
- UPEP (24-hr urine) and urine immunofixation
- Quantitative Ig levels
- Serum FLC
- Skeletal survey
- Plasmacytoma assessment

#### **6.1.2.2 Visit 2 (Cycle 1 Day 8 ± 1 day)**

- Adverse events
- Weight
- Vital signs
- Symptom-directed physical exam
- CBC with differential
- Complete serum chemistry

#### **6.1.2.3 Visit 3 (Cycle 1 Day 15 ± 1 day)**

- Adverse events
- Weight
- Vital signs
- Symptom-directed physical exam
- CBC with differential
- Complete serum chemistry

#### **6.1.2.4 Visit 4 (Cycle 2 Day 1 ± 2 days)**

- Medication dispensation
- Adverse events
- Concomitant medications
- Dose intensity
- QOL assessment
- Weight
- Vital signs
- Symptom-directed physical exam
- ECOG PS
- CBC with differential
- Complete serum chemistry
- Pregnancy test
- SPEP and serum immunofixation
- UPEP (24-hr urine) and urine immunofixation
- Quantitative Ig levels
- Serum FLC
- Skeletal survey\*
- Plasmacytoma assessment\*
- Bone marrow biopsy and aspirate\*

**6.1.2.5 Visit 5 (Cycle 2 Day 15 ± 2 days)**

- Adverse events
- Weight
- Vital signs
- Symptom-directed physical exam
- CBC with differential
- Complete serum chemistry

**6.1.2.6 Visit ≥ 6 (Cycle ≥ 3 Day 1 ± 2 days)**

- Medication dispensation
- Adverse events
- Concomitant medications
- Dose intensity
- QOL assessment
- Weight
- Vital signs
- Symptom-directed physical exam
- ECOG PS
- CBC with differential
- Complete serum chemistry
- Pregnancy test
- SPEP and serum immunofixation
- UPEP (24-hr urine) and urine immunofixation
- Quantitative Ig levels
- Serum FLC
- Skeletal survey\*
- Plasmacytoma assessment\*
- Bone marrow biopsy and aspirate\*

**6.1.2.7 End of Treatment Visit (≤ 14 days after last dose)**

- Adverse events
- Concomitant medications
- Dose intensity
- QOL assessment
- Weight
- Vital signs
- Complete physical exam
- ECOG PS
- CBC with differential
- Complete serum chemistry
- Pregnancy test
- SPEP and serum immunofixation
- UPEP (24-hr urine) and urine immunofixation
- Quantitative Ig levels

- Serum FLC
- Skeletal survey\*
- Plasmacytoma assessment\*
- Bone marrow biopsy and aspirate\*

### **6.1.3 Follow-up Phase**

#### **6.1.3.1 Follow Up Assessment (30 days after last dose ± 7 days)**

- Adverse events
- QOL assessment
- Telephone contact

#### **6.1.3.2 Duration of Response and Survival (every 3 months ± 14 days after last dose for 12 months)**

- Telephone contact
- SPEP and serum immunofixation
- UPEP (24-hr urine) and urine immunofixation
- Quantitative Ig levels
- Serum FLC
- Skeletal survey\*
- Plasmacytoma assessment\*
- Bone marrow biopsy and aspirate\*

## **7. Study Intervention**

### **7.1 Study Intervention/Device Description**

The following drugs will be used in this study:

#### **7.1.1 Selinexor**

Provided as coated, immediate-release 20 mg tablets for oral administration in wallet-sized blister packs. Karyopharm Therapeutics Inc. will supply selinexor at no charge and ship it to each site. Selinexor will be dispensed from the investigational pharmacy at each site and participants will be provided with only enough tablets for one cycle on the first day of each cycle. For information regarding storage, handling, precautions and contraindications, please refer to the package insert.

#### **7.1.2 Clarithromycin**

Patients will receive a prescription for clarithromycin 250 or 500 mg tablets (generic) for oral administration. Study participants will obtain this drug at their local pharmacy. For information regarding storage, handling, precautions and contraindications, please refer to the package insert.

#### **7.1.3 Pomalidomide**

Patients will receive a 21-day supply of pomalidomide 1, 2, 3, or 4 mg capsules for oral administration, as appropriate, for each 28-day treatment cycle. The investigator will enter an electronic prescription for pomalidomide after the study participant enrolls in the POMALYST REMS program. A specialty pharmacy will ship pomalidomide to the study participant's home. For information regarding storage, handling, precautions and contraindications, please refer to the package insert.

#### **7.1.4 Dexamethasone**

Patients will receive a prescription for dexamethasone 4 mg tablets (generic) for oral administration. Study participants will obtain this drug at their local pharmacy. For information regarding storage, handling, precautions and contraindications, please refer to the package insert.

### **7.2 Availability**

Selinexor is an FDA approved drug which will be supplied to investigators by Karyopharm Therapeutics Inc. Commercial co-therapies will be obtained by the study participant through retail and/or specialty pharmacies.

### **7.3 Acquisition and Accountability**

Selinexor will be provided by Karyopharm Therapeutics Inc. Commercial co-therapies will be obtained by the study participant. All co-therapies should be reimbursed by insurance or designated healthcare systems. Study drug accountability records will be maintained at the site pharmacy and will be available for review. Drug accountability is to be performed on selinexor only. "All-selinexor" accountability must be reviewed by the study monitor prior to destruction or return shipment.

The Investigator, or a responsible party designated by the Investigator, must maintain a careful record of the inventory and disposition of selinexor using the NCI Drug Accountability Record or another comparable drug accountability form. Available at the Cancer Therapy Evaluation Program website at <http://ctep.cancer.gov/> protocol development for the "Policy and Guidelines for Accountability and Storage of Investigational Agents".

Selinexor will be ordered through DRIVE, Endpoint's supply management engine. Drug ordering instructions have been provided by Karyopharm Therapeutics, along with recommended initial and resupply stock orders. Orders submitted via DRIVE will be filled by Karyopharm Therapeutics within 5 business days of receipt.

At the end of the study, unused supplies of selinexor should be destroyed according to institutional policies. Destruction will be documented in the Drug Accountability Record Form.

### **7.4 Formulation, Appearance, Packaging, and Labeling**

Selinexor is a Selective Inhibitor of Nuclear Export (SINE) compound. Selinexor specifically blocks nuclear export by binding to the nuclear export protein XPO1.

The chemical name is: (Z)-3-(3,5-bis(trifluoromethyl)phenyl)-1H-1,2,4-triazol-1-yl)-N-(pyrazin-2-yl)acrylohydrazide

The molecular formula is: C17H11F6N7O.

The molecular weight is: 443.31.

Each Selinexor drug container will be labeled in accordance with current International Conference on Harmonization (ICH), Good Clinical Practice (GCP), and specific regulatory requirements, e.g., FDA, Health Canada (HC), European Medicines Agency (EMA), etc. Containers for take-home use may require additional in-pharmacy labeling with take-home and patient-specific instructions (such as exact dose) depending on country-specific regulations or laws. All treatments will be labeled in accordance with current ICH, GCP, FDA, HC, and EMA regulations and guidelines. Labels will include the medication name, storage conditions, and batch number, and will comply with language and legal requirements of Canada, EU, and the US.

Selinexor will be supplied and administered as coated, immediate-release 20 mg oral tablets in wallet-sized blister packs.

Further information for Selinexor, as well as clarithromycin, pomalidomide and dexamethasone can be found on their respective package insert.

## **7.5 Product Storage and Stability**

Selinexor tablets should be stored in a locked and secured area with access restricted to the site staff pharmacist or designee(s) at or below 30°C (86°F). Room temperature storage is recommended, refrigerated is acceptable. Tablets should not be stored frozen.

Qualified personnel, familiar with procedures that minimize undue exposure to themselves and the environment, should undertake the preparation, handling, and safe disposal of the chemotherapeutic agent in a self-contained and protective environment.

Selinexor tablets are coated for ease of use and handling. Tablets should not be broken or crushed due to increased risk of dermal exposure and/or toxicities.

All other study medications should be stored as described on their respective package insert.

## **7.6 Preparation**

No special preparation required. Tablets of selinexor should not be crushed because of increased risk of dermatologic toxicity if powder comes in contact with skin.

## **7.7 Dosing and Administration**

For doses of study medication that are to be taken on non-clinic days, the patient will be provided with selinexor by the investigational pharmacy, and clarithromycin, pomalidomide and dexamethasone by their local and/or specialty pharmacy.

The doses of study treatments for individual patients should remain constant throughout the study, except for allowed dose modifications.

Study medications will be dosed according to the schedule provided below. For doses of oral medications to be taken on non-clinic days, patients will either be provided with medication to take home or with a prescription to obtain the medication from their local and/or specialty pharmacy.

Selinexor should be given with at least 120 mL (4 ounces) of fluids (water, milk, etc.).

Dexamethasone should be administered at least one hour before selinexor. In general, where possible, each drug should be given at least 1-2 hours apart, however the sequence and times of administration are per the Investigator's discretion.

Clarithromycin, pomalidomide, and dexamethasone should be administered in a manner consistent with each product's approved labeling.

Selinexor tablets should be swallowed whole (not crushed) to prevent an increased risk of dermatologic toxicity if the powder comes in contact with skin.

Missed doses of Selinexor should be managed as follows:

- If a dose was missed, the schedule of that week should be altered to accommodate one dose in that week with at least 36 hours between two consecutive doses.
- If a dose must be skipped (e.g., due to recommendation of treating physician), the next dose will be taken as per schedule. Doses should not be administered less than 36 hours apart and all missed and delayed doses should be documented.

If a patient missed a full one-week period of dosing for non-study drug-related events (e.g., a required medical procedure or an unanticipated personal emergency), the days missed will be replaced.

If a dose is vomited within 1 hour of ingestion, it will be replaced. If vomiting occurs more than 1 hour after dosing, it will be considered a complete dose.

All patients will receive selinexor, clarithromycin, pomalidomide and dexamethasone in 28-day cycles according to the following schedule:

Selinexor will be given orally at a dose of 60 mg on days 1, 8, and 15 of a 28-day cycle. Clarithromycin will be given orally at a dose of 500 mg twice a day on days 1-28 of a 28-day cycle.

Pomalidomide will be given orally at a dose of 4 mg daily on days 1-21 of a 28-day cycle.

Dexamethasone will be given orally at a dose of 40 mg on days 1, 8, 15 and 22 of a 28-day cycle.

#### **7.7.1 Dosing Delays/Dose Modifications**

In order to optimize specific anti-tumor activity and tolerability, dose reductions and/or schedule modifications will be allowed. Patients should also be treated aggressively with supportive care to reduce toxicities. Doses must be adjusted for adverse events deemed related to study drug by the Investigator. Doses may be adjusted for adverse events related to study medications not listed below at the discretion of the Investigator.

Toxicity will be graded according to CTCAE v.5.0; the therapy modifications described below are to be applied according to severity grading. If more than one type of AE occurs concurrently, the most severe grade will determine the modification. Each dose modification or treatment delay must be documented, including the respective reason. Re-escalation of selinexor is allowed as outlined in Table 3. If drug-related toxicity requires a treatment delay of more than 28 days, the patient will be taken off study treatment. For all  $\geq$  Grade 3 hematological or non-hematological AEs that are NOT selinexor related, after consultation with the Medical Monitor and at the discretion of the Investigator, selinexor dosing may be maintained.

Table 3 summarizes the study treatment dose levels; Table 4 describes supportive care and dose adjustment guidelines. General supportive care recommendations are provided below. Deviations from the guidelines are permitted after discussion between the PI and the treating physician.

In patients with renal impairment, start each drug at the following dose level:

- 1) Selinexor:
  - (a) CrCl  $\geq$ 15 mL/min: There are no dosage adjustments provided in the manufacturer's labeling.
  - (b) CrCl <15 mL/min: Patients with severe renal impairment are excluded from this study.
- 2) Clarithromycin:
  - (a) CrCl  $\geq$ 30 mL/minute: No dosage adjustment necessary.
  - (b) CrCl 15-29 mL/minute: Decrease clarithromycin dose by 50% by starting at dose level -1.
  - (c) CrCl <15: Patients with severe renal impairment are excluded from this study.
- 3) Pomalidomide:
  - (a) CrCl  $\geq$ 15 to <60 mL/minute: There are no dosage adjustments provided in the manufacturer's labeling. Compared to patients with normal renal function, pomalidomide pharmacokinetics were not significantly altered in patients with CrCl between 15 to 60 mL/minute.
  - (b) CrCl <15 mL/min: Patients with severe renal impairment are excluded from this study.
- 4) Dexamethasone:

(a) There are no dosage adjustments provided in the manufacturer's labeling. The International Myeloma Working Group (IMWG) recommendations suggest that dexamethasone may be administered without dosage adjustment in multiple myeloma patients with renal impairment.

In patients with hepatic impairment, start each drug at the following dose level:

- 1) Selinexor:
  - (a) Mild impairment: There are no dosage adjustments provided in the manufacturer's labeling; however, there are no clinically significant effects on selinexor pharmacokinetics.
  - (b) Moderate impairment: There are no dosage adjustments provided in the manufacturer's labeling (has not been studied).
  - (c) Patients with severe hepatic impairment are excluded from this study.
- 2) Clarithromycin:
  - (a) No dosage adjustment necessary if renal function is normal; however, in patients with hepatic impairment and concomitant severe renal impairment, a dosage reduction or prolonged dosing intervals may be appropriate, and patients should be started at dose level -1.
- 3) Pomalidomide:
  - (a) Mild or moderate impairment (Child-Pugh class A or B): Start at dose level -1 (3 mg once daily).
  - (b) Severe impairment (Child-Pugh class C): Patients with severe hepatic impairment are excluded from this study.
- 4) Dexamethasone:
  - (a) There are no dosage adjustments provided in the manufacturer's labeling.

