**Table 4. Supportive Care and Dose Adjustment Guidelines**

Toxicity	Grade	Dose Modification
Selinexor		

Fatigue	Grade 1 or Grade 2 lasting $\leq$ 7 days	
Maintain dose. Rule out other causes of fatigue, particularly dehydration and anemia. If found to be anemic, consider transfusing for Hb <math><</math> 8 g/dL.
 
Institute supportive care medications per institutional guidelines. Consistent with the National Comprehensive Cancer Network (NCCN) Clinical Practice Guidelines in Oncology (CPGO), the use of methylphenidate should be considered. Additional options are provided in the NCCN CPGO.
 
Patients with significant fatigue after several doses of selinexor may have an ongoing anti-tumor response. If fatigue is significant, consider assessment of tumor response as part of the patient's evaluation.

	Grade 2 lasting $>$ 7 days or Grade 3	
Interrupt selinexor dosing. Monitor until fatigue resolves to Grade 1 or baseline and restart selinexor at 1 dose level lower.
 
Institute supportive care medications as described above for Grade 1 or 2.
 
Patients with significant fatigue after several doses of selinexor may have an ongoing anti-tumor response. If fatigue is significant, consider assessment of tumor response as part of the patient's evaluation.

Anorexia or Weight Loss	Grade 1	
Maintain dose. Rule out other causes of anorexia. Nutritional consultation can be helpful.
 
Consider instituting supportive care medications per institutional guidelines.
 
Consistent with the NCCN CPGO, megestrol acetate 200-400 mg twice daily should be considered. Other options are provided in the NCCN CPGO.

	Grade 2	
Rule out other causes of anorexia and order a nutritional consultation.
 
Institute supportive care medications as described for Grade 1 anorexia or weight loss above. For additional options, see NCCN CPGO.
 
Interrupt dosing with selinexor until improves to Grade 1 or baseline and weight stabilizes, then restart selinexor at 1 dose level lower.

	Grade 3	
Nutritional consultation and supportive care medications for anorexia per institutional guidelines should already be instituted. For additional options, see NCCN CPGO.
 
Interrupt dosing with selinexor until improves to Grade 1 or baseline and the weight stabilizes. Restart selinexor at 1 dose level reduction.

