Nausea and/or Vomiting	Grade 1 or 2	
Maintain dose. Rule out other causes of nausea.
 
Patients should be receiving 5HT3 antagonists unless contra-indicated. For those patients who cannot receive 5HT3 antagonists, consider olanzapine per NCCN CPGO. For additional options, see NCCN CPGO.

		If intolerable or persistent Grade 2, follow guidelines for Grade 3.
Hyponatremia	Grade 3	
Supportive care medications per institutional guidelines should already be instituted. For additional options, see NCCN CPGO.
 
Interrupt selinexor dosing until resolved to Grade <math>\leq</math> 2 or baseline. Restart selinexor at 1 dose level lower.
 
If nausea stabilizes for at least 4 weeks at Grade <math>\leq</math> 1, may re-escalate to the original dose after consulting Medical Monitor.

	Grade 1	
Maintain dose. Rule out other causes including drug (e.g., diuretic) effects. Be certain that reported sodium level is corrected for concurrent hyperglycemia (serum glucose <math>> 150</math> mmol/L).
 
Treat hyponatremia per institutional guidelines including dietary review. Consider addition of salt tablets to patient's diet.

	Grade 2	
Correct for hyperglycemia as outlined under Grade 1.
 
Treat hyponatremia per institutional guidelines. If (corrected) sodium is Grade <math>\leq</math> 3 and continues to be asymptomatic, then patient may continue current dosing provided that intravenous saline and/or salt tablets (1-3 times daily) are provided.
 
If Grade 2 is persistent or worsens or does not respond to treatment, dose interruptions may be considered after consulting with the Medical Monitor.

	Grade 3 or 4	
Treat per institutional guidelines. Delay selinexor until sodium resolved to Grade <math>\leq</math> 1 (<math>\geq 130</math> mmol/L) then reduce selinexor dose by 1 level. If serum sodium stabilizes to Grade <math>\leq</math> 1 for at least 4 weeks, may re-escalate to previous dose of selinexor.

Diarrhea	Grade 1 or 2	
Initiate treatment for any Grade 1 diarrhea. Treat per institutional guidelines with antidiarrheals and maintain dosing.
 
For persistent Grade 2 only that does not respond to anti-diarrheals within 3 days, interrupt selinexor dosing until resolved to Grade 1, then restart at the current dose level.

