	Grade 3 or 4	
Delay selinexor until resolved to Grade 1, then reduce selinexor dose by 1 dose level.
 
If diarrhea stabilizes for at least 4 weeks at Grade <math>\leq</math> 1, may re-escalate to previous dose of selinexor after consulting with the Medical Monitor.

Thrombocytopenia	Grade 1	Maintain dose.
	Grade 2 or 3 without bleeding	
Consider platelet growth factors, e.g., romiplostim, which may take up to four weeks for an effect.
 
Reduce selinexor at 1 dose level lower.
 
Patients with stable platelet counts for <math>\geq</math> 4 weeks following dose reduction may have their dose of selinexor increased by one dose level.

	Grade 4 without bleeding	Strongly consider platelet growth factors and transfuse per clinical practice/institutional guidelines. Delay dosing until recovery to $\leq$ Grade 2 or baseline and resume selinexor at 1 dose level lower.
	Grade 2 or 3 with bleeding	Delay dosing until the bleeding has stopped and the patient is clinically stable. Reduce selinexor at 1 dose level lower.
Neutropenia	Grade 3 or 4 Neutropenia without fever	Institute colony stimulating factors, and delay dosing with selinexor until ANC returns to Grade $\leq$ 2. Reduce selinexor by 1 dose level. After stabilization for at least 4 weeks, a re-escalation may be considered after discussing with the Medical Monitor.
	Grade 3 or 4 Neutropenia with fever	Institute colony stimulating factors, and delay dosing with selinexor until the patient's ANC returns to Grade $\leq$ 2 or baseline, fever has resolved, and patient's condition is stable. Reduce selinexor by 1 dose level.
Anemia	Grade 3	Treat per institutional guidelines including blood transfusions and/or erythropoietins. Consider transfusing for Hb $<$ 8 g/dL. Reduce selinexor by 1 dose level.
	Grade 4	Treat per institutional guidelines including blood transfusions and/or erythropoietins. Consider transfusing for Hb $<$ 8 g/dL. Delay dosing of selinexor until Hb is 8 g/dL or higher. Reduce selinexor by 1 dose level.
Ocular Toxicity	Grade 2, excluding cataract	Perform ophthalmologic evaluation. Interrupt selinexor and provide supportive care. Monitor until ocular symptoms resolve to Grade 1 or baseline. Restart selinexor at 1 dose level lower.
	Grade 3 or 4, excluding cataract	Permanently discontinue selinexor. Perform ophthalmologic evaluation.

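### Section 7.7.1 lets the highest-grade adverse event set the dose change, but Table 4 is not ordered by grade across event types, so for some same-drug pairs a required hold is dropped

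*Combined protocol and SAP*

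**What the plan says.** Section 7.7.1 of the combined protocol and SAP grades toxicity by CTCAE v5.0, applies the Table 4 modifications by grade, and settles concurrent AEs with one sentence: "If more than one type of AE occurs concurrently, the most severe grade will determine the modification". The closing line of Table 4 ties all modifications to the worst toxicity that came before, without defining worst.

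The relevant selinexor rows of Table 4 are:

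- Anorexia or weight loss, Grade 2: "Interrupt dosing with selinexor until improves to Grade 1 or baseline and weight stabilizes, then restart selinexor at 1 dose level lower".
- Fatigue, Grade 2 beyond 7 days or Grade 3, after interruption: "Monitor until fatigue resolves to Grade 1 or baseline and restart selinexor at 1 dose level lower".
- Ocular toxicity, Grade 2: "Interrupt selinexor and provide supportive care. Monitor until ocular symptoms resolve to Grade 1 or baseline", then restart one level lower. Grade 3 or 4: "Permanently discontinue selinexor. Perform ophthalmologic evaluation".
- Diarrhea, Grade 2, not responding to treatment within 3 days: "interrupt selinexor dosing until resolved to Grade 1, then restart at the current dose level".
- Anemia, Grade 3: supportive treatment, with transfusion considered when hemoglobin is below "8 g/dL. Reduce selinexor by 1 dose level". There is no interruption. Grade 4: "Delay dosing of selinexor until Hb is 8 g/dL or higher. Reduce selinexor by 1 dose level".

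For dexamethasone, agitation, confusion or another psychiatric disorder of Grade 2 or higher means a hold and a restart at the next lower level. Edema or hyperglycemia of Grade 3 or higher means a one-level reduction with dosing continued.

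Section 7.7.1 also allows departures from the guidelines once the treating physician has discussed them with the PI.

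**The concern.** A tie-break by grade presumes that a higher grade always carries at least as strict an action. Table 4 sets actions by AE type as well as by grade, and across types for one drug the order sometimes reverses. In those pairs a patient with two toxicities is handled less cautiously for that drug than a patient with only the milder one. At stake are doses given while a toxicity that Table 4 treats as a reason to stop dosing is still present. No text says that the stricter action prevails, so the safer course depends on sites departing from the stated rule.

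**Working it through.** The plan gives no figure to reproduce. The check sets Table 4 rows side by side for one drug, then converts the lost holds to dose using Table 3.

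**Pairs, with both AEs attributed to the drug**

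| Drug | Lower-grade AE alone | Higher-grade AE | Literal rule |
|---|---|---|---|
| Selinexor | Grade 2 anorexia, ocular toxicity, or fatigue >7 days: interrupt, then one level lower | Grade 3 anemia: reduce only | Hold lost |
| Dexamethasone | Grade 2 confusion or agitation: hold, then one level lower | Grade 3 edema or hyperglycemia: reduce only | Hold lost |
| Selinexor | Grade 3 ocular toxicity: discontinue permanently | Grade 4 anemia: delay, then reduce | Conditional |
| Selinexor | Persistent Grade 2 diarrhea: interrupt, restart at same dose | Grade 3 anemia: reduce only | Mixed |

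The first two lines are clear cases: the rule drops the hold and adds nothing in return. Grade 3 thrombocytopenia without bleeding is also reduce-only for selinexor. It triggers a pomalidomide hold as well (Table 4; Section 7.7.1.2), which partly offsets the loss for the regimen, so it is not counted as clear.

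**Inputs from Table 3.** Selinexor 60 mg on Days 1, 8 and 15, so 3 × 60 = 180 mg planned per cycle; level -1 is 40 mg. Dexamethasone 40 mg on Days 1, 8, 15 and 22, so 4 × 40 = 160 mg; level -1 is 20 mg. I assume a full Day 1 dose, later onset, and a single one-level reduction.

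**Higher-grade AE corrected within about a week.** It then no longer outranks the AE that requires a hold, and about one reduced dose is given that should have been withheld.

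- Selinexor: 40/180 = 22.2 points.
- Dexamethasone: 20/160 = 12.5 points.

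**Both AEs keep their grades to cycle end.**

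- Selinexor, onset between Days 1 and 8: rule 60 + 40 + 40 = 140 mg, hold 60 mg; 80/180 = 44.4 points.
- Selinexor, onset between Days 8 and 15: 160 versus 120 mg; 40/180 = 22.2 points.
- Dexamethasone, onset between Days 1 and 8: 40 + 20 + 20 + 20 = 100 mg versus 40 mg; 60/160 = 37.5 points.
- Dexamethasone, onset between Days 8 and 15: 120 versus 80 mg; 25 points.
- Dexamethasone, onset between Days 15 and 22: 140 versus 120 mg; 12.5 points.

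**Relative dose intensity.** Section 12.4.3 averages over cycles. About 10 months of treatment (Section 1) is 304.4/28 = 10.87 cycles. One affected cycle then shifts a patient's value by 22.2/10.87 = 2.0 to 44.4/10.87 = 4.1 points for selinexor, and by 12.5/10.87 = 1.1 to 37.5/10.87 = 3.4 points for dexamethasone.

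**Conditional pair.** Selinexor is withheld until hemoglobin reaches 8 g/dL. If the eye event is still Grade 3 at that point, it has become the highest grade and its row requires permanent discontinuation. Selinexor is wrongly resumed only if the eye event falls below Grade 3 first. Only then does each later full cycle carry 3 × 40 = 120 mg instead of 0, or 120/180 = 66.7 points.

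**Mixed pair.** Diarrhea alone means a hold and a return to 60 mg. With anemia, the rule gives 40 mg without a hold. The hold is lost but a reduction is gained.

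**The case against.** Several counter-arguments carry weight.

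- **Discretion.** Table 4 is titled as guidelines, deviations are allowed after PI discussion, and Sections 7.9 and 8.2 let the investigator stop treatment or withdraw a patient. Many investigators would take the safer action. This stands as mitigation, but it makes the safer action the exception to the written rule.
- **Other text.** The note after Table 4 lets 1 or 2 selinexor doses be skipped for combinations of Grade 1 or 2 AEs, which does not cover a Grade 3 partner. Sections 7.7.1.1 to 7.7.1.3 cover only thrombocytopenia and neutropenia. Section 7.8.14 blocks the next Day 1 for confusion above Grade 1, so it confines that case to one cycle. It has no hemoglobin criterion and accepts Grade 2 anorexia, fatigue or ocular toxicity, so it does not stop the selinexor pairs.
- **Attribution.** Adjustment is mandatory only for AEs judged related to study drug, and selinexor may be maintained for unrelated AEs of Grade 3 or higher. Myeloma itself causes anemia. If the anemia is not attributed to selinexor, the Grade 2 row should govern. This stands as a condition.
- **Persistence.** The higher-grade rows prescribe correction: transfusion or erythropoietins, diuretics, insulin. The upper dose figures therefore need toxicities that resist treatment.

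A reader might infer that the rule overrides permanent discontinuation for Grade 3 ocular toxicity whenever Grade 4 anemia is present, or that it picks the weaker action in every pair listed. The documents support neither: the anemia row already withholds selinexor, and in the diarrhea pair the rule is stricter on dose level.

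**Conclusion.** The tie-break is defective as written. For selinexor with Grade 3 anemia, and for dexamethasone with Grade 3 edema or hyperglycemia, it drops a hold that Table 4 requires for a concurrent Grade 2 AE. This rests on both AEs being attributed to the same drug and on sites following the sentence literally.

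The consequence is mainly one or more missed holds within a cycle, and both routes lead to the same lower dose level. About one dose is the reasonable figure; 44 and 37.5 points are upper bounds. The ocular pair is a conditional risk, and the diarrhea pair only shows that actions must be combined rather than ranked.

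Frequency cannot be estimated. Section 2.4.1.4 reports fatigue (52%), anemia (45%) and anorexia (36%) with weekly selinexor, pomalidomide and dexamethasone, but without grades for these events or joint timing, and the documents give no ocular toxicity rate. Nothing here touches the two-stage design, type I error, power or the ORR analysis. Severity is minor to moderate.

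**What to change.** Replace the tie-break sentence in Section 7.7.1 with:

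*If more than one AE occurs concurrently, apply for each study drug every Table 4 action triggered by any AE attributed to that drug: discontinue if any AE requires it; otherwise hold if any AE requires it, until the recovery criteria of all AEs requiring a hold are met; then resume or continue at the lowest dose level required by any of the AEs.*

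Make the closing line of Table 4 refer to this rule for concurrent AEs. Leave Sections 7.7.1.1 to 7.7.1.3, the provision for AEs unrelated to selinexor, and the permitted deviations as they are.

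Combining actions is better than ranking them as discontinue, hold, reduce, maintain. For persistent Grade 2 diarrhea with Grade 3 anemia, a ranking would choose the diarrhea hold and restart at 60 mg, losing the reduction. The combined rule holds until diarrhea is Grade 1 and resumes at 40 mg.

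The cost is two sentences in an amendment and a memo to sites, with no new data or patients. The downside is somewhat more and longer holds. A few could exceed the 28-day limit for coming off treatment in Section 7.7.1, or the matching four-week limit on cycle delay in Section 7.8.14.
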